- Change in reported general health
- Change in BMI, weight, or waist circumference

Handling of Missing Values

There will likely be missing values related to incomplete or missing surveys. Participants will only be included in the analysis if they completed at least 50% of weekly surveys during each time period: baseline, supplementation, and washout. Values will be binned longitudinally such that each participant included in the analysis has a data point associated with each bin. If there are multiple values associated with a participant in a bin, the mean of those values will be used for the analysis.

Statistical Procedures

The majority of primary and secondary endpoints for this study are questions on the survey which consist of rating scales (generally 1-5 or 1-9). Significant differences between groups for these endpoints will be assessed using an independent T test or Mann-Whitney U test depending on the observed

distribution of the data. For significant changes over time within the same group, a dependent T test will be used.

For differences between groups in terms of primary and secondary endpoints that measure a change in time (e.g. time to recovery in days or hours of sleep), an independent T test or Mann-Whitney U test will be used, depending on the observed distribution of the data. For significant changes over time within the same group, a dependent T test will be used.

To identify demographics associated with any particular response (benefit or side effects), we will use the demographic, health history, and lifestyle information collected in the surveys to build an unsupervised machine learning algorithm (e.g. Random Forest Classifier). If we can build one that effectively classifies the response (AUC > 0.7), we will identify the model's most important features. To confirm that these features are significantly associated with response, we will use an independent T test to assess significant differences between response and non-response.

For all other exploratory endpoints including the optional fitness tracker data, the data type and distribution of that data will determine the statistical analysis used.

Measures to Adjust for Confounders

For all data and endpoints, data can be normalized to the baseline collected values, and change in value at different time points can be compared using the statistical tests described above.

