In addition, there is a question included in the weekly surveys assessing how participants are generally feeling about their life, which they respond to using a rating scale from 1 (pessimistic) to 9 (optimistic). If necessary, we can normalize the weekly survey data using this rating to confirm that participant life and stress outside the study are not affecting how they respond to the surveys.

QC Plans

All analyses will be performed by a study bioinformatician or data scientist. All code used for the analysis will be saved using version control software such as Git in the format of Python notebooks. These notebooks will be reviewed by other study staff for errors and certified that analyses are correct prior to any written or oral reports, presentations, or publications on the results of the study.

Programming Plans

All code for these analyses will be written using Python 3 in Jupyter notebooks. The pandas library will be used for importing the data, manipulating it in a data frame, and exporting it as excel or comma-separated files. The Numpy and Scipy libraries will be used for all statistical analysis and the Sci-Kit Learn library will be used for machine learning analyses. Matplotlib and Seaborn libraries will be used for visualization of the data as graphs and charts.

Investigator Conflict of Interest

Investigators will disclose any conflict of interest.

Any investigator who has a conflict of interest with this study (patent ownership, royalties, or financial gain greater than the minimum allowable by their institution, etc.) must have the conflict reviewed by a properly constituted Conflict of Interest Committee with a Committee-sanctioned conflict management

plan that has been reviewed and approved by the study Sponsor prior to participation in this study. All investigators will follow the conflict of interest policy.

References

3. Gross K, Santiago M, Krieger JM, Hagele AM, Zielinska K, Scheiman J, et al. *Acute Impact of Veillonella atypica FB0054 Supplementation on Exercise Performance and Lactate Changes: A Randomized, Crossover Pilot.* *Nutrients. In Review.*

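### The AUC > 0.7 rule for naming responder traits is not required to be out-of-sample, and the T test meant to confirm those traits is not said to use separate data

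*Combined protocol and SAP*

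**What the plan says.** The Statistical Procedures section of the Biostatistical Analysis Plan describes a three-step search, introduced with "To identify demographics associated with any particular response (benefit or side effects".

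1. Survey items on demographics, health history and lifestyle are used to "build an unsupervised machine learning algorithm (e.g. Random Forest Classifier". A Random Forest classifier is in fact a supervised method, so that label needs correcting.
2. A threshold decides whether traits are named: "If we can build one that effectively classifies the response (AUC > 0.7".
3. A test follows: "To confirm that these features are significantly associated with response, we will use an independent T test".

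Programming Plans adds only that "the Sci-Kit Learn library will be used for machine learning analyses". QC Plans adds a review of the notebooks for errors. No section mentions a hold-out set, cross-validation, out-of-bag estimate, permutation test or confidence interval for the AUC. None defines response, fixes the number of responses to be modelled, or gives an alpha or multiplicity correction for the T test.

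**The concern.** An AUC threshold separates signal from noise only if the AUC is measured on participants the model has not seen. A forest with default settings grows each tree until it reproduces its own training labels, so its AUC on those data is close to 1 whether or not any trait matters. The wording allows that AUC to be used. The T test does not repair this if it is run on the same participants, because traits chosen for looking associated in a data set tend to look associated when tested in it again. The code review would not necessarily catch either problem, since neither is a coding error.

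The Data Management and Analysis Objectives sections make it an aim of the study to say which participants benefit or have side effects. The sections on return of results and intended use foresee publications, promotional material and help with participants' later purchases. Artefact traits could reach all of these.

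**Working it through.** The plan has no figure to reproduce: 0.7 is a decision rule, and no sample size, alpha or expected AUC is given for this analysis. The check is what the rule does when no trait is related to response.

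**From the documents.** Threshold, example model and T test: Statistical Procedures. Library, without settings: Programming Plans. Number of candidate traits: not given; Table 1 lists 18 sign-up and 31 baseline questions, 18 + 31 = 49. Response rate: not given; Risk/Safety Information puts the commonest side effects at 1 in 10 or more. Number analysed: not given; Recruitment expects up to 1,000 invited.

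**Assumed.** 200 to 800 analysed; 30 or 49 traits; response in 10%, 30% or 50%; 100 trees with scikit-learn defaults, then minimum leaf sizes of 20 and 50; the library's default (impurity) importance; T test two-sided at 0.05.

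**Step 1: why the in-sample AUC is 1.** With N = 200, a participant enters a tree's bootstrap sample with probability 1 − (1 − 1/200)^200 = 0.633, and a fully grown tree then returns that participant's own label. Under noise with 30% response, a responder scores on average about 0.633 + 0.367 × 0.3 = 0.74 and a non-responder about 0.367 × 0.3 = 0.11. The two groups separate without any signal.

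**Step 2: simulation under pure noise.** With 30 traits the mix was 15 yes/no items, 13 five-level items, age and a BMI-like variable.

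| N | Traits | Response | Min. leaf | Data sets | In-sample AUC, mean (min) | 5-fold CV AUC, mean | CV > 0.7 | 30% hold-out > 0.7 | At least 1 of top 5 with p < 0.05 |
|---|---|---|---|---|---|---|---|---|---|
| 800 | 30 | 30% | 1 | 40 | 1.000 (1.000) | 0.505 | 0% | 0% | 53% |
| 200 | 30 | 30% | 1 | 80 | 1.000 (1.000) | 0.500 | 0% | 0% | 56% |
| 800 | 30 | 10% | 1 | 40 | 1.000 (1.000) | 0.514 | 0% | 0% | 55% |
| 200 | 30 | 10% | 1 | 80 | 1.000 (1.000) | 0.508 | 1.3% | 5.0% | 55% |
| 800 | 49 | 50% | 1 | 30 | 1.000 (1.000) | 0.502 | 0% | 0% | 70% |
| 800 | 30 | 30% | 20 | 30 | 0.903 (0.880) | 0.511 | 0% | 0% | 70% |
| 800 | 30 | 30% | 50 | 30 | 0.763 (0.743) | 0.511 | 0% | 0% | 90% |

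The in-sample AUC exceeded 0.7 in every data set of every row. A second series (N = 300 and 600; 10% and 30% response; 5 continuous, 10 five-level and 15 yes/no traits) gave an in-sample AUC of 1.000 in all 240 runs. Its cross-validated AUC averaged 0.49 to 0.51, with a maximum of 0.60.

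**Step 3: one small hold-out.** The null SD of an AUC is sqrt((n1 + n0 + 1)/(12 n1 n0)). The 30% hold-out at N = 200 and 10% response has n1 = 6 and n0 = 54: sqrt(61/3888) = 0.125, z = 0.2/0.125 = 1.6, P(AUC > 0.7) = 0.055. The simulated 5.0% agrees. A single split is therefore weak for rare responses.

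**Step 4: the T test on the same data.** Five unselected independent traits give 1 − 0.95^5 = 22.6% for at least one p < 0.05. The table shows 53% to 90%, with 12% to 30% of top-five traits significant. With the trait mix of the second series (200 data sets per setting) the figure was 20% to 28%, and 4.5% to 5.8% per trait. Further runs over trait mixes and leaf sizes gave 18% to 83%. The 90% is 27 of 30 data sets, so its standard error is sqrt(0.9 × 0.1/30) = 5.5 points.

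The spread has a likely cause. In the second series the mean importance was about 0.086 per continuous and 0.014 per yes/no trait, which leaves (1 − 5 × 0.086 − 15 × 0.014)/10 = 0.036 per five-level trait. The five continuous traits tend to fill the top five whatever their association, so the T test behaves as if on unselected traits. With only two continuous traits, the other places go to whichever traits happen to look associated. Either way the ranking is unreliable: it follows measurement scale or chance.

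**The case against.** The strongest reply is that the SAP is silent rather than wrong. A reader might infer that it calls for an in-sample AUC and that the threshold therefore cannot separate signal from noise. The documents do not support that: no data source for the AUC is stated, and an analyst who cross-validates would almost never pass noise. This stands, and the point is limited to what the rule permits.

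A reader might also infer that artefact traits are certain to be reported. That skips the T test, which blocks some of them; with one plausible trait mix it confirms none of the top five in 72% to 80% of noise data sets. This too stands, although blocking at the rate expected for unselected traits is not independent confirmation.

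A third tempting step is to compound a false-pass rate over all 16 listed endpoints. Analysis Objectives confines the search to differences that have been observed, the endpoints are plainly related, and the per-response hold-out rate depends heavily on sample size and response rate. No such product is justified.

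The T test itself suits yes/no traits: it disagreed with the uncorrected chi-square at 0.05 in 0.025% of 4,000 simulations. The objection to it covers only multi-level nominal traits given integer codes, and the SAP does not say how traits are coded.

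Finally, the analysis reads as exploratory, and Analysis Objectives is worded tentatively. That lowers the stakes but does not excuse calling the last step confirmation.

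**Conclusion.** The concern holds in this form. The threshold that triggers the naming of traits is not required to be out-of-sample, and the test described as confirming them is not said to use other data. Where the AUC is taken on the fitting data, noise passed in 100% of simulated data sets, including those with constrained trees. Taken by cross-validation, it passed in 0% in six of the seven tabulated settings and 1.3% in the smallest. After a same-data T test, at least one false trait among the top five survives in roughly 20% to 80% of data sets for a single response; one constrained setting with few runs reached 90%. Artefact traits are thus possible to likely, not certain.

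The pass result held over every sample size, trait count, response rate and leaf size tried. The survival figure depends strongly on the assumed trait mix, forest settings and importance measure. The flaw touches only the search for responder traits, so it should be corrected before analysis, but it does not threaten the comparison between arms.

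**What to change.** Amend Statistical Procedures to state the following.

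- Response is defined in advance for each benefit or side effect to be modelled, and every response tried is counted and reported.
- The AUC comes from repeated stratified cross-validation, with all tuning and feature selection inside the folds.
- Traits are named only if that AUC exceeds 0.7 and a permutation p-value, corrected for the number of responses tried, is below 0.05.
- Traits are ranked by permutation importance on the held-out folds.
- Selected traits are tested only in data not used to select them, for example a stratified part of the sample locked away before modelling, with a stated alpha and multiplicity correction. Chi-square or Fisher tests are used for multi-level nominal traits. If no data are set aside, the word confirm is dropped and estimates are given descriptively.
- Results are labelled exploratory, and the Random Forest is described as supervised.

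The cost is SAP wording and a few lines of code in a library already named; no new data need be collected. The downside is that fewer traits will be reported, and setting data aside leaves less for model building. The between-arm analyses do not change.

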The informed consent process will include a privacy authorization compliant with 45CFR164.508(c) via the inclusion/incorporation of:

- all core elements specified in 508(c)(1) including the signature of the individual (or representative) and date of signature,
- all required statements specified in 508(c)(2)
- the plain language requirement as specified in 508(c)(3), and
- the provision to the participant (or representative) a copy of the signed authorization (508(c)(4)

State of California Human Experimentation Requirements

This research involves the collection of information via validated questionnaires and obtaining information from the medical record. Research activities do not encompass those that are requisite for a participant to be involved in a “medical experiment” as defined by California State Law 24174. The ‘California Experimental Subject’s Bill of Rights’ will be administered as part of the informed consent process; as part of that process participants will receive a copy of the ‘Bill of Rights’ marked with their signature.

Data Management

Study data will be stored in secure password-protected servers. Study staff will de-identify all data prior to data analysis. Data will be analyzed to compare the safety and efficacy of Veillonella vs placebo and between the two different doses of Veillonella. We will also use these data to better understand the type of benefits different subsets of participants tend to experience as well as the magnitude of the benefit in these subpopulations. These results will be used to create peer-reviewed publications, academic and industry presentations, file patents, and potentially develop new innovative microbiome products like probiotics. Participants will not be notified of any of these uses.

Confidentiality

All documents and electronic data will be stored on secure, password-protected computers. Participant confidentiality will be strictly held in trust by the investigators, study personnel, and sponsor. No identifiers will be used in any subsequent publication of these results.

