The publication or presentation of any study results shall comply with all applicable privacy laws, including, but not limited to, the Health Insurance Portability and Accountability Act of 1996. Neither the complete nor any part of the results of the study carried out under this protocol, nor any of the information provided by the sponsor for the purposes of performing the study, will be published or passed on to any third party without the written approval of the Study PI. Any investigator involved with this study is obligated to provide the sponsor with all data derived from the study.

Biostatistical Analysis Plan

Data Source

The source of the data is the results of the questionnaires filled out through the Chloe app as well as the optional fitness tracker data collected over the course of the study.

Analysis Objectives

The goals of this analysis are to identify whether there are statistically significant differences in effects between the placebo and Veillonella groups as well as between the high and low dose Veillonella groups. Furthermore, for any differences that are observed, we would like to understand whether there are any demographic or other participant characteristics that may be associated with benefits or side effects experienced by the participants.

Analysis Sets / Populations / Subgroups

The three groups compared in this study are high dose Veillonella, low dose Veillonella, and placebo.

In addition, we plan to separately analyze results by gender, age, baseline exercise habits, health history, previous probiotic experience, sleep habits, and other lifestyle factors.

For those participants who share fitness tracker data, the fitness tracker data shared through the Chloe app will be analyzed in conjunction with survey data separately from those who did not share fitness tracker data.

Endpoints

The primary endpoints analyzed in this study are:

- Change in reported physical fatigue
- Change in mental / emotional fatigue
- Change in MFI

The secondary endpoints analyzed in this study are:

- Change in reported sleep quality
- Change in frequency of reported physical activity
- Change in intensity of reported physical activity
- Change in reported exercise
- Change in recovery time
- Change in energy level

The exploratory endpoints analyzed in this study are:

- Changes in fitness tracker data
- Change in reported bowel movements
- Change in GSE
- Change in reported mood
- Change in reported digestive health

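### The responder classifier and its t-test have no placebo contrast, so they can link traits to response but not to a larger benefit of Veillonella over placebo

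*Combined protocol and SAP*

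**What the plan says.** Statistical Procedures gives the aim of the step as "To identify demographics associated with any particular response (benefit or side effects", benefits and side effects alike. Demographic, health-history and lifestyle answers are used to "build an unsupervised machine learning algorithm (e.g. Random Forest Classifier". The next sentence sets a gate, "If we can build one that effectively classifies the response (AUC > 0.7", after which the most important features are read off. Then comes "To confirm that these features are significantly associated with response, we will use an independent T test", comparing those with a response to those without. Treatment arm is not listed as an input, a stratum or a contrast, and the text does not say which arms enter.

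Three other places bear on what the step is for:

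- Data Management wants to learn which benefits different subsets experience and "the magnitude of the benefit in these subpopulations".
- Analysis Objectives, straight after naming the placebo and dose comparisons, says that "for any differences that are observed, we would like to understand whether there are any demographic or other participant characteristics" may be associated with benefits or side effects.
- Analysis Sets / Populations / Subgroups adds that "we plan to separately analyze results by gender, age, baseline exercise habits, health history" and further factors. No test of whether the treatment effect differs between subgroups is named there or elsewhere in the Biostatistical Analysis Plan.

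**The concern.** The size of a benefit in a subpopulation is a difference from placebo. The endpoints are largely self-reported ratings, so some participants will improve without any action of the product, and some traits will predict that improvement. A comparison of responders with non-responders treats such a trait in the same way as one that changes the effect of Veillonella.

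At stake is the follow-on question of who benefits and by how much. A trait of people who improve anyway could be reported as a trait of people whom Veillonella helps. The section on data retention, future use and sharing allows the study data to be used in promotional material, so the distinction matters beyond the analysis team.

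**Working it through.** The plan gives no power, alpha or effect-size figure for this step, so there is nothing to reproduce.

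**Inputs from the documents.** Allocation is 4:4:2, so 80% active and 20% placebo (Details Study Procedures). Up to 1,000 invitations are estimated (Recruitment). The gate is AUC > 0.7 (Statistical Procedures).

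**Assumptions.** Two-sided 0.05; residual SD 1; arm effect 0.2 SD; response = the top 35% of change; 400 or 1,000 analysed. Of these, 1,000 is an upper case, because "Participants will only be included in the analysis if they completed at least 50% of weekly surveys during each time period".

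**Step 1: two traits that differ only on placebo.** Trait A has slope 0.2 SD per SD in every arm. Trait B has slope 0.2 on Veillonella and 0 on placebo. In the active arms both follow change = 0.2 + 0.2x + error, so no analysis confined to those arms can separate them. Simulated rejection rates (4,000 trials), for a trait that has reached the test:

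| Test | A, n=400 | B, n=400 | A, n=1,000 | B, n=1,000 |
|---|---|---|---|---|
| t-test, active arms | 78% | 78% | 99% | 99% |
| t-test, arms pooled | 87% | 70% | 100% | 98% |
| arm-by-feature interaction | 5% | 36% | 5% | 70% |

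Pooling the arms flags the true modifier, B, less often than A. A rerun gave 71% for the last entry.

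**Step 2: interaction power by formula.** SE of the slope difference = √(1/(0.8n) + 1/(0.2n)) = √(6.25/n) = 2.5/√n.

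- n=400: SE 0.125; 0.2/0.125 = 1.60; power Φ(1.60 − 1.96) = 36%.
- n=1,000: SE 0.0791; 0.2/0.0791 = 2.53; power Φ(2.53 − 1.96) = 72%.
- Ten features, Bonferroni level 0.005 (critical value 2.807): Φ(1.60 − 2.807) = 11% and Φ(2.53 − 2.807) = 39% (38% simulated).

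**Step 3: the gate.** At slopes 0.1, 0.2 and 0.3 a trait like A has a single-trait AUC of about 0.55, 0.59 and 0.63. At slope 0.2 it exceeded 0.7 alone in 0 of 2,000 trials at either sample size. The t-test rates in Step 1 are therefore conditional on other features opening the gate and on this trait being selected. A stronger trait can open it alone. With one purely prognostic feature (log odds 1.2 per SD, n=1,000, 20 features), mean out-of-bag AUC was about 0.73. That feature ranked first and was significant by t-test in 40 of 40 runs, while its interaction with arm was significant in 1 of 40.

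**Step 4: separate subgroup analyses.** Take two equal halves with the same true effect d, doses pooled. In each half, SE = √(1/(0.4n) + 1/(0.1n)) = √(12.5/n). With power p per half, exactly one half is significant with probability 2p(1 − p).

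- n=400: SE 0.177. d=0.2: p=0.20, giving 33%. d=0.3: p=0.40, giving 48%.
- n=1,000: SE 0.112. d=0.2: p=0.43, giving 49%. d=0.3: p=0.76, giving 36%.

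Significance in one subgroup and not in the other is thus common when the effect does not differ at all.

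**The case against.** The strongest reply is that the step promises no more than association. Statistical Procedures speaks only of features associated with response, and Analysis Objectives uses association wording too. That stands. The mismatch is with the Data Management goal and, on a natural reading, with the opening of the Analysis Objectives sentence. A reader might infer that the plan itself claims effect modification from the forest; it does not.

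Second, the subgroup analyses may already include placebo comparisons. That also stands, but Step 4 shows why they do not settle whether the effect differs.

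Third, the 78% and 99% might be read as the rate at which the plan as written would flag trait A. The documents do not support that, because the AUC gate comes first (Step 3).

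Fourth, a reader might infer that testing selected features on the same data fills the results with false confirmations. The plan names no second sample, so the t-test cannot be called an independent confirmation, but this rests on silence about a split. With an out-of-bag gate open and a mix of binary, five-level and continuous features, noise features were confirmed about 6% of the time each (95% CI 5% to 8%), no clear excess. With all-continuous features it was 19%, so the size depends on feature type. It is not a main claim here.

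The missing definition of response and of how the AUC is computed is absent detail. Calling a classifier unsupervised is a slip of wording, since the method is named.

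**Conclusion.** The concern holds in a limited form. Followed as written, the step cannot show which traits go with a larger Veillonella-over-placebo benefit, and no other named analysis tests this. That conclusion is structural and depends on no assumed number. The rates illustrate its size and rest on the assumed slopes, alpha, responder share and numbers analysed; the t-test rates hold only once the gate is open and the trait selected. The primary comparisons of Veillonella with placebo are not affected, and nothing here suggests otherwise. This is a cheap improvement that should be made before the data are analysed.

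**What to change.** 1. For any statement about who benefits, and for the planned subgroup analyses, add a regression of the endpoint on arm (both doses against placebo), feature, their product and the baseline value. Use the logistic analogue for side effects. Test the product term, with Holm adjustment over a list of features named in advance.
2. Report the forest and t-test results only as associated with response and hypothesis-generating, not as confirmed modifiers of the Veillonella effect.

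The cost is SAP wording and modest code, with no new data. The model has to be added, because the plan names only t-tests and Mann-Whitney tests for comparing groups. The drawback is power. For a 0.2 SD slope difference it is about 36% at 400 and 71% at 1,000 for one feature, and 11% and 38% at the Bonferroni level for ten, which Holm can only improve on. A non-significant interaction should therefore not be read as evidence that the benefit is the same for everyone.

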- Have a significant acute or chronic coexisting illness, disorder, or condition that contraindicates, in the Principal Investigator's judgment, entry to the study.
- Currently taking immunosuppressive medications.
- Is considered immunosuppressed for any reason.
- Currently taking medications that could impair the integrity of the gut epithelia
- Has symptoms or an illness, disorder, or cognition that impairs the integrity of the gut epithelia.
- Current antibiotic use or planned oral antibiotic use over the course of the study.
- Investigator believes that the participant may be uncooperative and/or noncompliant and should therefore not participate in the study.

Research equity

This research has no direct exclusions related to gender. There are also no direct exclusions related to race or ethnicity.

Vulnerable Populations

Vulnerable populations are not specifically targeted in this research. Racial and ethnic minorities will be included in the participants but are not specifically targeted for inclusion.

Study Procedures

See Figure 1 for details of study procedures.

Recruitment

Participants will be recruited to the study via email and social media. Interested participants will sign up through the online study landing page. Participants will be chosen from the pool of signups based on the

inclusion and exclusion criteria above. There is no maximum number of participants. All those eligible will be invited to participate. However, we estimate up to 1,000 participants will be invited to participate in the study.

Details Study Procedures

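### The plan confirms every model-selected trait with a T test whatever its data type; for an unordered trait with three or more levels held as one coded column, the result depends on the arbitrary codes

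*Combined protocol and SAP*

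**What the plan says.** The Statistical Procedures section of the Biostatistical Analysis Plan describes a model, with a random forest classifier as the example, built on the "demographic, health history, and lifestyle information collected in the surveys". It continues: "If we can build one that effectively classifies the response (AUC > 0.7), we will identify the model's most important features". The final step is that "we will use an independent T test to assess significant differences between response and non-response".

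The plan does not list the candidate traits item by item. The Analysis Sets / Populations / Subgroups section names characteristics of the same kind: "gender, age, baseline exercise habits, health history, previous probiotic experience, sleep habits, and other lifestyle factors".

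Three neighbouring provisions matter:

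- Rating-scale and time endpoints may be analysed by T test or Mann-Whitney U, depending on the observed distribution.
- For the other exploratory endpoints, "the data type and distribution of that data will determine the statistical analysis used".
- The Programming Plans section says that "the Sci-Kit Learn library will be used for machine learning analyses" and that Numpy and Scipy will do the statistical analysis.

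Neither flexible rule is extended to the trait step. The plan does not state how categorical answers are coded, which form of the T test is meant, or the significance level.

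**The concern.** A T test compares means. That suits age, and it is tolerable for many ordered scales. It also works for a yes/no item, where the mean is a proportion. It does not suit an unordered item with several levels, such as a type of condition or a type of exercise. The mean of arbitrary level numbers has no meaning there, and two analysts who number the levels differently can reach opposite conclusions from the same data.

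Finding participant characteristics associated with benefit or side effects is a stated analysis objective. This test is the last step before a trait is called significantly associated. A real association could therefore be lost, or its detection could turn on a numbering choice that the plan does not record.

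**Working it through.** The plan gives no sample size, power or error rate for this step, so there is no figure to reproduce. The check uses assumed cases with two-sided alpha 0.05 (also assumed).

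**Inputs.** The Recruitment section says "we estimate up to 1,000 participants will be invited to participate in the study". With 4:4:2 allocation, at most 1,000 × 8/10 = 800 would take Veillonella, so N = 800 is used. The category count, response rates and prevalences are assumptions, because the questionnaires are not in the documents.

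**1. Unordered trait, five equal categories, response 45% in one and 30% in the other four.**

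- Overall response = (0.45 + 4 × 0.30)/5 = 0.33, giving 264 responders and 536 non-responders.
- Share of responders in the affected category = 0.45/1.65 = 0.273, and in each other category 0.30/1.65 = 0.182.
- Share of non-responders in the affected category = 0.55/3.35 = 0.164, and in each other category 0.70/3.35 = 0.209.

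*T test, affected category coded 2 on codes 0-4.* The distribution is symmetric about 2 in both groups, so both mean codes are exactly 2.00. The difference is 0 and power equals the alpha level of about 5% (simulation: 4-5%).

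*T test, affected category coded 4.* Mean code in responders = 0.273 × 4 + 0.182 × (0+1+2+3) = 2.18. Mean code in non-responders = 0.164 × 4 + 0.209 × 6 = 1.91. The difference is 0.271. With pooled SD 1.41, the standard error is 1.41 × √(1/264 + 1/536) = 0.106, so z = 2.56. Power ≈ Φ(2.56 − 1.96) = 73% (simulation: 71-73%).

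*Chi-square, any coding.* Noncentrality = 800 × 0.2 × (0.12² + 4 × 0.03²)/(0.33 × 0.67) = 160 × 0.018/0.2211 = 13.0 on 4 degrees of freedom. Power is 84% (simulation: 82-84%).

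*T test on a 0/1 indicator for the affected category.* Difference = 0.273 − 0.164 = 0.109. Standard error = √(0.2 × 0.8 × (1/264 + 1/536)) = 0.0301, so z = 3.61. Power is 95%, or about 84-85% after Bonferroni for five indicators. Indicator coding removes the problem.

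**2. One fixed table under every coding.** In an illustrative four-level trait (250 responders split 90/40/40/80, 500 non-responders split 120/130/130/120), the T test p-value ranged from 0.000001 to 0.81 over the 24 possible codings. It was below 0.05 in 12 of them. Chi-square gave p = 0.000005 throughout.

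**3. Yes/no trait.** The same data coded 0/1, 1/2 or 7/4 gave p = 0.2046 each time, and Pearson chi-square gave 0.2037. Coding has no effect.

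**4. Rare yes/no trait, no true association.** Take 40 people with a side effect, 760 without, and 3% prevalence in both. Exact enumeration gives these false-positive rates:

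| Test | Rate |
|---|---|
| T test, unequal variance (Welch) | 29.7% |
| T test, pooled | 4.4% |
| Fisher's exact | 2.6% |

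The Welch figure arises almost entirely when none of the 40 has the trait, which has probability 0.97^40 = 0.296. The small group then has zero variance. The standard error comes only from the large group; with 23/760 it is 0.0062, so t = 0.0303/0.0062 = 4.9. Of the 29.7 points, 29.6 show the trait as less common among those with the side effect.

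The effect needs both a small group and a rare trait. At N = 800 and prevalences of 0.5% to 5%, the Welch error is 4.1-4.8% with a 50:50 split, 5.4-9.6% with 30% responders and 8.9-41.6% with 10% responders. The pooled test stays at 4.0-5.3% throughout.

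**The case against.** The strongest reply is that the damage depends on choices the plan has not made. Nothing says that a multi-level item will be held as one integer column. If it is expanded into 0/1 indicators, which a scikit-learn workflow allows, each selected feature is binary and the T test behaves almost like chi-square. This stands as a limit on the point. It does not remove the point, because the plan fixes neither the encoding nor an alternative test, and so permits the poor result.

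A reader might infer three stronger things that the documents do not support.

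- *Most candidate traits are categorical.* Item formats are not shown. Age is numeric, and exercise and sleep items may be numeric or ordinal.
- *The T test fails for rare yes/no traits.* Only the unequal-variance form does so, and only with a small response group. The plan does not name that form, and the pooled form was the default in the SciPy installation used for this check.
- *The test would falsely flag rare conditions as risk factors for side effects.* Even under Welch, nearly all the false positives point the other way.

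It is also fair to say that the AUC threshold and importance ranking come first, which the calculations ignore, and that a very rare trait is an unlikely top feature. A separate weakness of the same step, that no independent data are named for the confirmation, would remain whichever test is used.

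**Conclusion.** The point holds in a limited form. One test is prescribed for traits of any data type. For an unordered trait with three or more levels kept as a single coded column, that test gives a result that depends on the numbering. Under the assumed five-category case, power is about 4-5% or 71-73% according to the code, where chi-square gives about 82-84%. These figures rest on the assumed N, categories and rates. The mechanism requires only that at least one selected trait be of this kind.

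Yes/no traits and indicator-coded traits are not affected by coding. The rare-trait problem (about 30% false positives at 40 vs 760 and 3% prevalence) is conditional on the unequal-variance form and consists almost wholly of spurious inverse associations. The step lies outside the primary and secondary between-group comparisons, so the consequence is modest and the change is desirable rather than essential.

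**What to change.** In Statistical Procedures, replace the single T test for model-selected traits with a test matched to the trait:

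- chi-square for categorical traits;
- Fisher's exact test for sparse 2×2 tables;
- T test or Mann-Whitney U for numeric or ordinal traits.

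Alternatively, specify one logistic regression of response on the trait, with categorical traits entered as factors and a likelihood-ratio test. Under either option, state how categorical items are coded for the model. If a T test is kept for numeric traits, state which form is used.

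The cost is a few lines of SAP wording. No new data are needed, and SciPy, which the plan already names, provides the chi-square and Fisher tests.
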